14.4 Safety

Safety data will be presented as summary and descriptive statistics, and will be provided for actual values and change from baseline values for vital signs

The incidence and severity of AEs reported during the study and their relationship to study drug will be tabulated. AEs will be coded using the Medical Dictionary for Regulatory Activities (MedDRA™) and the CTCAE v 4.03, and will be presented by body system and preferred term.

The World Health Organization Drug Dictionary (WHODD) will be used to classify prior and concomitant medications by therapeutic class and preferred term. Prior and concomitant medication usage will be summarized by the number and percentage of subjects receiving each medication within each therapeutic class.

Safety analyses will be presented by age group (pediatric and adult) and for all subjects.

14.5 Preliminary Efficacy

Efficacy will not be assessed in this trial. However, summary statistics on the daily dose of baclofen and changes in dose of baclofen will be summarized in the clinical study report.

15.0 DATACOLLECTION, STUDY MONITORING, AND DATA DISCLOSURE

15.1 Data Collection and Reporting

A CRF will be completed for each subject who receives at least one dose of study drug. All entries on the CRF must be supported by original source documentation (e.g., laboratory reports, medical records) maintained at the investigational site.

The Investigator will review all safety assessments (AEs, vital signs, and results from physical examinations) on an ongoing basis. The Investigator is required to review all entries on the CRF and sign at appropriate time intervals.

15.2 Study Monitoring

All aspects of the study will be monitored carefully by the Sponsor's designees with respect to current Good Clinical Practice and Standard Operating Procedures for compliance with applicable government regulations. It is the responsibility of the Investigator to provide all study records, including CRFs, source documents, etc., for review and inspection by the clinical monitor.

All CRFs will be 100% source verified against corresponding source documentation (e.g., office and clinical laboratory records) for each subject. Clinical monitors will evaluate periodically the progress of the study, including the verification of appropriate consent form procedures, review of drug accountability and preparation procedures, adherence to dosing procedures, and the verification of the accuracy and completeness of CRFs. Clinical monitors will also ensure that all protocol requirements, applicable FDA regulations, other requirements, and Investigator's obligations are being fulfilled.

15.3 Data Disclosure and Subject Confidentiality

Subject medical information obtained as a result of this study is considered confidential. Disclosure to third parties other than those noted below is prohibited. All reports and communications relating to subjects in this study will identify each subject only by their initials and number. Medical information resulting from a subject's participation in this study may be given to the subject's personal physician or to the appropriate medical personnel responsible for the subject's welfare. Data generated as a result of this study are to be available for inspection

on request by FDA or other government regulatory agency auditors, the Sponsor clinical monitor (or designee), and the IRB/EC.

All laboratory specimens, evaluation forms, reports, and other records that leave the site will be identified by a coded number to maintain subject confidentiality. All records will be kept in a locked file cabinet. All computer entry and networking programs will be identifiable only by coded numbers. Clinical information will not be released without written permission from the subject, except as necessary for monitoring by the IRB, the FDA, or the study Sponsor.

Any information, inventions, or discoveries (whether patentable or not), innovations, suggestions, ideas, and reports, made or developed by the Investigator(s) as a result of conducting this study shall be promptly disclosed to the Sponsor and shall be the sole property of the Sponsor. The Investigator agrees, upon the Sponsor's request and at the Sponsor's expense, to execute such documents and to take such other actions, as the Sponsor deems necessary or appropriate, to obtain patents in the Sponsor's name covering any of the foregoing.

The results of this study will be published under the direction of the Sponsor. Results will not be published without prior review and approval by the Sponsor.

16.0 PROTECTION OF HUMAN SUBJECTS

16.1 Declaration of Helsinki

The study will be conducted in accordance with the Declaration of Helsinki (1964) including all amendments up to and including the South Africa revision (1996).

16.2 Institutional Review Board/Ethics Committee

The Investigator agrees to provide the IRB/EC with all appropriate material, including a copy of the Informed Consent Form. The study will not be initiated until the Investigator obtains written approval of the research plan and the Informed Consent Form from the appropriate IRB/EC and copies of these documents are received by the Sponsor. Appropriate reports on the progress of this study will be made by the Investigator to the IRB/EC and Sponsor in accordance with applicable government regulations and in agreement with the policies established by the Sponsor. The Sponsor ensures that the IRB/EC complies with the requirements set forth in [21 CFR Part 56](#).

Appendix A. Schedule of Study Procedures

Appendix A: Schedule of Study Procedures: Screening through Single-Dosing Period

Study Procedure	Screening	Baseline ^a	Visit Schedule ^b							
			Based on 6-Month Refill ^c							
Study Day	Day -14 to -1	Day -3 to 1	6-Month	9- Month	12-Month	18-Month	24-Month	30-Month	36-Month	
Signed informed consent	X									
Medical history	X									
Compete physical exam	X									
Targeted physical exam*		X	X	X	X	X	X	X	X	
Vital signs ^d	X	X	X	X	X	X	X	X	X	
Weight ^d	X	X	X	X	X	X	X	X	X	
Concomitant medication assessment	X	X	X	X	X					
Adverse event assessment			X	X	X	X	X	X	X	
Gabufen® 3 mg/mL administration		X^e								
Clinical evaluation for Inflammatory Granulomas ^f	X	X	X	X	X	X	X	X	X	

* A targeted physical exam is defined as a limited examination for the cause and severity of a reported adverse event to assess the need for medical intervention. A general examination is not necessary.

a. Baseline evaluations must be performed within 72 hours prior to Gabufen 3 mg/mL administration on Day 1. Baseline and Screening visit may be combined. SOC assessments performed prior to informed consent may be incorporated from the medical history into study data, if not performed exclusively for this clinical trial.

b. All study visits are ± 7 days from scheduled date.

c. For subjects that require refills more frequently than every 6-months due to the daily dose of baclofen, a customized Appendix A schedule may be requested from the Medical Monitor.

d. For vital signs and weight, a best effort should be conducted to obtain these data. If obtaining these data is not possible due to subject cooperation, the effort should be documented and results recorded as "not evaluable" (NE).

e. Administration of Gabufen 3 mg/mL will start on Day 1 of the study.

f. If there are clinical signs of an inflammatory granuloma as defined in [Section 3.3](#), the Medical Monitor should be notified and an MRI scheduled to confirm the pathology of the granuloma.

Appendix B. National Cancer Institute Common Terminology Criteria for Adverse Events

Version 4.03

Publication Date: 14 June 2010

http://evs.nci.nih.gov/ftp1/CTCAE/CTCAE_4.03_2010-06-14_QuickReference_8.5x11.pdf

[figure not shown]

10.6. Pregnancies (as applicable).....	14

10.7. Other Safety Measures	14
10.7.1. Physical Examination.....	14
10.7.2. Medical History	14
10.7.3. Vital Signs.....	14
10.8. Statistical Method for Analysis of Safety and Demographic data.....	14
10.8.1. Wilcoxon Signed-rank Test.....	14
10.8.2. 95% Confidence Interval.....	15
11. REFERENCES.....	15

Trademark Information

Trademarks not owned by MALLINCKRODT PHARMACEUTICALS, INC.
SAS®

LIST OF ABBREVIATIONS

ABBREVIATION	DEFINITION
AE	Adverse event
CFR	Code of Federal Regulations
cGMP	Current Good Manufacturing Practices
CSF	Cerebral Spinal Fluid
CNS	Central nervous system
CO ₂	Carbon dioxide
CRF	Case report form
CRU	Clinical research unit
CTCAE	Common Terminology Criteria for Adverse Events (v. 4.03)
EC	Ethics Committee
ECG	Electrocardiogram
g	Gram
GABA	Gamma-aminobutyric acid
GCP	Good Clinical Practice(s)
ICF	Informed Consent Form
ICH	International Conference on Harmonization
Incidence	Number of subjects with one or more events
IRB	Institutional Review Board
IT	Intrathecal Injection
IP	Investigational Product
kg	Kilogram
L	Liter
MedDRA	Medical Dictionary for Regulatory Activities
MFD	Maximum Feasible Dose
mg	Milligram
mL	Milliliter

ABBREVIATION	DEFINITION
MRI	Magnetic Resonance Imaging
NCI	National Cancer Institute
NDA	New Drug Application
PI	Principal Investigator
Rate	Number of events adjusted for a unit of time
SAP	Statistical Analysis Plan
SAE	Serious Adverse Event
USP	United States Pharmacopeia
WHODD	World Health Organization Drug Dictionary

1. INTRODUCTION

This statistical analysis plan (SAP) supports the evaluation of the protocol outcomes and planned assessments while 3 mg/mL concentration of Gablofen® (baclofen injection) is administered to subjects.

The purpose of this statistical analysis plan (SAP) is to describe the planned analyses of the safety and frequency of inflammatory granuloma from a 3 mg/mL formulation of Gablofen® (baclofen injection). All analyses, quality control procedures, and data displays will follow the Global Statistical Group's standard operating procedure.

The content of this SAP is based on the revised protocol CNS-GAB101US version 2.0 (18 December 2014). Further information can be found in the study protocol.

2. STUDY OBJECTIVES AND ENDPOINTS

2.1. Study Objectives

The primary objective of this safety and post-approval surveillance study is to obtain data on the rate of inflammatory granulomas in patients given Gablofen® (baclofen injection) 3mg/mL by the intrathecal route of administration.

The secondary objective is to evaluate the overall safety data on 3 mg/mL Gablofen® (baclofen injection) given by the intrathecal route of administration.

2.1.1. Study Endpoints

2.1.1.1. Primary Endpoint

The primary endpoint is the rate of confirmed inflammatory granulomas after the first 12-months of therapy following the initiation of treatment with a 3 mg/mL formulation of Gablofen® (baclofen injection).

A confirmed inflammatory granuloma or mass is one where there are clinical signs and symptoms of an inflammatory granuloma, and an intradural extra-medullary mass is verified by an MRI with contrast enhancement. If only clinical signs and symptoms are identified, and no other assignable cause can be identified, the event will be recorded as a possible inflammatory mass.

All MRI-confirmed granulomas will be evaluated by a central independent radiologist as a routine trial procedure per the protocol.

Incidence is defined as the number of subjects with one or more events.

The rate of inflammatory granulomas will be evaluated based on 0 to 9 months, 0 to 12 months, and > 12 months of therapy.

For 0 to 9 months and 0 to 12 months of therapy, rate will be defined as:

$$\text{Rate} = I_T / (N_T + G_T)$$

Where:

I_T = Number of subjects with an inflammatory granuloma within the time interval

N_T = Number of subjects who reach the end of the time interval

G_T = Number of subjects with inflammatory granuloma who discontinue prior to reaching the end of the time interval

For > 12 months of therapy, rate will be defined as:

$$\text{Rate} = I_{>12} / N_{>12}$$

Where:

$I_{>12}$ = Number of subjects with an inflammatory granuloma after 12 months of therapy

$N_{>12}$ = Number of subjects who reach beyond 12 months of therapy

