4. PLANNED ANALYSES

4.1. Interim Analysis

Two interim analyses will be conducted when 100 subjects reach nine (9) months of therapy and when 100 subjects reach twelve (12) months of therapy.

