5. SAMPLE SIZE CONSIDERATIONS

5.1. Sample Size Determination

Up to 150 subjects will be enrolled at up to fifteen investigative sites. The sample size for this study is not based on statistical considerations. The sample size was selected to ensure that 100 subjects will remain in the study for 12-months of evaluation.

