10.3. Clinical Evaluation for Inflammatory Mass

The incidence (number of subjects with one or more events), frequency and rate of inflammatory granulomas will be summarized for 0 to 9 months, 0 to 12 months, and > 12 months of therapy. All inflammatory granulomas data will be listed for each subject and data from any SAE reports relating to inflammatory granulomas will be summarized in full detail.

A summary of the incidence and frequency of inflammatory granulomas by classification (Confirmed and possible) will also be presented.

These analyses will be performed for both the ITT and PP populations. The ITT population will be the primary analysis population.

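### At the 9- and 12-month interim analyses the SAP's granuloma rate can be overstated, because a case in a subject still short of month 9 or 12 is counted while event-free subjects with the same follow-up are not

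*SAP*

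**What the plan says.** SAP 2.1.1.1 gives the rate for 0–9 and 0–12 months as I_T/(N_T + G_T). The numerator, I_T, takes in anyone found to have a granuloma inside the window. The denominator is built from two groups. One, N_T, is the "Number of subjects who reach the end of the time interval". The other, G_T, brings back cases that leave the trial early, and is worded as the "Number of subjects with inflammatory granuloma who discontinue prior to reaching the end of the time interval". It has no counterpart for event-free subjects.

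On timing, SAP 4.1 states: "Two interim analyses will be conducted when 100 subjects reach nine (9) months of therapy and when 100 subjects reach twelve (12) months of therapy". On size, SAP 5.1 states: "Up to 150 subjects will be enrolled at up to fifteen investigative sites". The aim is to keep 100 subjects for 12 months.

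On population, SAP 10.3 states for the granuloma analyses: "The ITT population will be the primary analysis population". SAP 6 defines ITT as eligible, consented and treated with 3 mg/mL, with no minimum follow-up. Protocol 3.3.1 has subjects with a detected granuloma discontinued from the trial, so a case before month T normally falls in G_T.

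Neither document limits I_T or G_T to subjects who could have reached month T by the data cut. Neither gives a censoring or person-time method. SAP 8.1 rules out imputation.

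**The concern.** At an interim cut some subjects may simply not have been in the study long enough to reach month T. Whether such a subject enters the rate depends on outcome. With a granuloma, the subject is counted in I_T, and in G_T once discontinued. Without one, the subject is counted nowhere, although observed for just as long. A case found just before the cut and not yet discontinued would be in the numerator and missing from the denominator.

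This matters because the granuloma rate is the primary endpoint and no hypothesis is tested (SAP 2.2), so the estimate and its 95% CI are the result. The 12-month interim gives the first figure on that endpoint, and Protocol 1.4 intends the 12-month safety data to support the marketing application. If a pending subject has a case, the reported rate depends partly on how fast later subjects were enrolled. It would then move at the final analysis as those subjects enter N_T.

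**Working it through.** The plan has no rate or powered sample size to reproduce ("The sample size for this study is not based on statistical considerations"). The only planning arithmetic is 150 enrolled for 100 completers, which implies up to 1 − 100/150 = one-third dropout. No dropout rate is stated.

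**Inputs.** From the documents: the formula, the trigger of 100 subjects at month T, and the maximum of 150. Assumed: all 150 enrolled evenly over 12 months (about 48 months of study less 36 of follow-up); a constant hazard of 1 granuloma per 100 patient-years; every case discontinued; exponential dropout of fraction d by month 12, so μ = −ln(1 − d)/12.

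**12-month look, no dropout.** Accrual is 12.5 per month. The 100th subject starts at about month 8, so the cut falls at about month 20. The other 50 have a mean of about 9.97 months.

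- Patient-years: 100 in mature subjects, 50 × 9.97/12 = 41.5 in pending subjects.
- Expected cases: 1.000 + 0.415 = 1.415.
- SAP formula: 1.415/(100 + 1.415) = 1.40%.
- Restricted to subjects with 12 months of potential follow-up: 1.000/(100 + 1.000) = 0.99%.
- Ratio 1.41, or +41%.

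**9-month look, no dropout.** Mean pending follow-up is 6.97 months, so pending cases are 0.01 × 50 × 6.97/12 = 0.290. SAP: 1.040/101.040 = 1.03%. Restricted: 0.750/100.750 = 0.74%. Inflation +38%.

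**With dropout.** Expected person-months for a subject with potential follow-up f are (1 − e^(−μf))/μ. The cut is the first time the expected number reaching T is 100.

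| Dropout by month 12 | 12-month look | 9-month look |
|---|---|---|
| 0% | +41% | +38% |
| 10% | +29% | +31% |
| 20% | +18% | +22% |
| 30% | +5% | +13% |
| one-third | 0% | about +10% |

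At one-third dropout, 150 × 2/3 = 100, so the 12-month trigger is met only when the last enrollee reaches month 12 and nobody is pending.

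**A different follow-up pattern.** With 100 full-window subjects and pending follow-up spread uniformly from 0 to T, simulation put the mean SAP rate at about 1.05, 1.12 and 1.24 times the true risk for 10, 25 and 50 pending subjects. The ratio was about 1.00 with none pending or after restriction. If 50 pending subjects were all just short of month T at 1% risk, it would be (150 × 0.01)/(100 + 50 × 0.01)/0.01 = 1.49.

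**How often it bites.** At the 12-month look with no dropout, the chance of any case among pending subjects is 1 − e^(−0.415) = 34% at the assumed hazard. Treating the 0.27% in Protocol 1.1 (12 of 4,384 pump patients) as a yearly rate gives 41.5 × 0.0027 = 0.112, and 1 − e^(−0.112) = 11%.

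**Worked case.** Take 150 treated, 100 event-free at month 12, 48 event-free and pending (follow-up uniform over 0–12 months), and two cases at month 4, one of them in a pending subject. SAP: 2/102 = 1.96%. Restricted: 1/101 = 0.99%. Kaplan-Meier: at month 4, 100 + 32 + 2 = 134 are at risk, so 2/134 = 1.49%.

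**The case against.** A reader might infer that the interim rate will be too high, by something like 41%. The documents do not support that. The top figure needs full enrolment and no dropout, whereas the sample size itself allows for up to one-third dropout, where the 12-month effect disappears. The inflation is also an expectation: if no pending subject has a granuloma, the SAP formula and the restricted one give the same rate and CI. Protocol 1.1 reports no granulomas in 1,283 baclofen patients, so that is the likelier outcome. These points stand and limit the claim.

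Other outputs soften the harm. SAP 10.3 lists every case. SAP 10.8.2 also plans a 95% CI for the percentage of subjects with an event. No threshold or stopping rule hangs on the rate, and an error upward is the cautious direction for a safety endpoint. This lowers the stakes but does not correct the primary figure.

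Two passages could be read as a restriction. SAP 3 ties the second interim to a first cohort of 100, but that sets timing and redefines none of the three counts. Protocol 14.2 limits the granuloma assessment to subjects completing 12 months, which conflicts with the SAP's ITT rule without repairing it. In the per-protocol set, which requires at least 12 months of therapy, early discontinued cases drop out and the bias runs the other way.

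The case missing from the denominator altogether is a brief edge case, given the discontinuation provision in Protocol 3.3.1.

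**Conclusion.** The concern holds in conditional form. As written, the ITT interim rate is biased upward in expectation whenever subjects are still short of month T at the cut, and the reported number changes only if one of them has a granuloma. Under the stated accrual and hazard assumptions the relative inflation is 0% to +41% at the 12-month look and about +10% to +38% at the 9-month look, depending on dropout. The documents do not give the number pending, so no single figure within those ranges can be claimed. Pending subjects affect the interims only. The omission of event-free dropouts from the denominator is a separate matter that persists at the final analysis.

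**What to change.** In SAP 2.1.1.1, state that at each interim the 0–9 and 0–12 month granuloma risk is estimated in the ITT population by Kaplan-Meier with a 95% CI, censoring event-free subjects at the data cut or at discontinuation. All cases and all follow-up are then used. Because zero cases is a likely result and the usual Kaplan-Meier variance then gives no interval, name a fallback, such as an exact binomial limit on subjects followed to month T (0/100 has an upper 95% limit of 3.62%).

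As a minimum, if I_T/(N_T + G_T) is kept, count all three terms at each interim only among subjects whose first 3 mg/mL dose was at least T months before the cut, and list and narrate cases in later enrollees beside the rate.

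The cost is a short SAP amendment and slightly more programming, with no added subjects or visits. The minimal version has two drawbacks. Cases in later enrollees stay outside the interim rate until their cohort matures, and event-free dropouts remain excluded. In the model above the true 12-month risk is 1 − e^(−0.01) = 0.995%, and the restricted formula gives 1.108% at 20% dropout and 1.187% at 30%, about 11% and 19% too high. Kaplan-Meier avoids both drawbacks, provided dropout is unrelated to granuloma risk.

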Efficacy Analysis	There is no efficacy measure in this open-label clinical trial. However, the dose of baclofen intrathecal will be monitored during the trial.
Study Duration	It is planned that each subject will participate in the study for a minimum of 12 months with an extension for up to 24 additional months permitted at the discretion of the patient and attending physician. Overall duration of the study will be approximately 48 months, depending on the rate of enrollment and number of subjects enrolled.
Study Centers	Up to fifteen (15) investigative sites will participate in the study.

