3.2 Study Endpoints

3.2.1 Primary Endpoint

The primary endpoint is rate of definite inflammatory granulomas during the first 12-months of therapy following the initiation of treatment with a 3 mg/mL formulation of Gablofen® (baclofen injection).

A confirmed inflammatory granuloma or mass is one where there are clinical signs and symptoms of an inflammatory granuloma, and an intradural extra-medullary mass is verified by enhancement on an infusion MRI. If only clinical signs and symptoms are identified, and no other assignable cause can be identified, the event will be recorded as a possible inflammatory mass.

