3. STUDY DESIGN

This is a prospective twelve-month Phase IIIb clinical safety trial followed by 2-year, Phase IV study that will be conducted at 10 to 15 clinical trial sites that are experienced with the use of intrathecal baclofen. All subjects will be entered after signing an IRB approved informed consent. Subjects will be followed for the duration of their treatment with Gablofen® (baclofen injection) 3 mg/mL using the SynchroMed® II Programmable Pump or until the study is terminated. Subjects will be evaluated for clinical complications associated with the use of intrathecal baclofen that are considered signs and symptoms of an inflammatory granuloma, specifically new radicular pain at the level of the catheter tip, and/or spinal cord compression. Case report forms will be collected from the investigator at every clinical monitoring visit for the first 12 months for each subject enrolled and then every 6 months thereafter. If there are any signs or symptoms identified which may indicate an inflammatory granuloma formation, an MRI scan with and without infusion will be performed (with consent of the subject) to evaluate the potential presence of an inflammatory granuloma. Events that may be related to an inflammatory granuloma will be classified as definite granuloma, possible granuloma, or other catheter related problem (confirmed not caused by a granuloma) or other clinical sequelae caused by the underlying disease or infusion system related event. An interim analysis will be conducted when 100 subjects on the 3 mg/mL concentration of Gablofen® (baclofen injection) reach 9 months of treatment. Additionally, a second interim analysis will be completed after the first cohort of 100 subjects reach 12 months. Thereafter, annual safety reports will be generated as part of this 3 year program and a final study report completed when all subjects complete 36-months of treatment.

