10.8. Statistical Method for Analysis of Safety and Demographic data

10.8.1. Wilcoxon Signed-rank Test

The Wilcoxon signed-rank test is a non-parametric statistical hypothesis test for the case of two related samples or repeated measurements on a single sample. It can be used as an alternative to the paired Student's *t*-test when the population cannot be assumed to be normally distributed. Like the paired or related sample *t*-test, the Wilcoxon test involves comparisons of differences between measurements, so it requires that the data are measured at an interval level of measurement. However, it does not require assumptions about the form of the distribution of the measurements. It should therefore be used whenever the distributional assumptions that underlie the *t*-test cannot be satisfied. This test will be used to test the difference between baseline and visit in case the variables are continuous. SAS code such as that below will be used to fit the method described above:

```
PROC UNIVARIATE;  
  VAR chage;  
  RUN;
```

10.8.2. 95% Confidence Interval

The incidence (number of subjects with one or more events) of inflammatory granulomas, suspected granulomas, and other catheter related events will be summarized and a 95% CI of the percent of subjects with one or more events will be presented. The rate of subjects with inflammatory granulomas for 0 to 9 months, 0 to 12 months and > 12 months therapy period will be summarized including a 95% CI of the mean rates. Results will be summarized in the three planned interim reports and included in the overall study final report at the end of 3 years.

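### The SAP's granuloma rate contains no time: after month 12 it ignores how long subjects were followed, and before month 12 it drops event-free leavers

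*SAP*

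**What the plan says.** The primary objective in both documents is to obtain data on the rate of inflammatory granulomas. The SAP's abbreviation list defines a rate as "Number of events adjusted for a unit of time" and, separately, incidence as a number of subjects. SAP 10.3 and 10.8.2 report the two as different outputs.

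SAP 2.1.1.1 then gives two formulas:

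- **0-9 and 0-12 months:** I_T / (N_T + G_T). I_T is the number of subjects with a granuloma in the interval, N_T is "Number of subjects who reach the end of the time interval", and G_T is the number of cases who discontinue before the interval ends.
- **>12 months:** I_>12 / N_>12. The denominator is "Number of subjects who reach beyond 12 months of therapy".

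The protocol synopsis describes at least 12 months of participation, "with an extension for up to 24 additional months permitted at the discretion of the patient and attending physician". Protocol 3.2.1 limits the primary endpoint to the first year: "The primary endpoint is rate of definite inflammatory granulomas during the first 12-months of therapy". SAP 10.3 makes ITT the primary population for granulomas, and SAP 8.1 includes a leaver's results up to withdrawal. SAP 10.8.2 summarises the rates for all three periods, "including a 95% CI of the mean rates", and names no method. Neither document plans a person-time or Kaplan-Meier estimate. SAP 10.1 gives exposure only as a by-subject listing plus a dose summary.

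**The concern.** Every term in both formulas is a head count, so neither meets the SAP's own definition of a rate. The consequences differ by period.

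**After month 12 (main defect).** The interval has no fixed length. A subject who stays one day past month 12 and one who stays two years each add 1 to the denominator. The result is neither a rate nor a risk over a stated period. It depends on how much follow-up has accrued at the data cut and on how long subjects choose to stay.

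**0-9 and 0-12 months (lesser defect).** These windows are fixed, so the ratio can be read as an approximate risk. But an early leaver enters the denominator only if a case. Event-free leavers and their observed time drop out, which sits badly with ITT as primary and with SAP 8.1.

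The study tests no hypothesis (SAP 2.2), so the estimate and its interval are the whole product. If few or no granulomas occur, the upper limit is the main result, and after month 12 that limit would not reflect the follow-up behind it.

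**Working it through.** The documents state no expected granuloma rate, and SAP 5.1 says the sample size has no statistical basis, so there is no planned figure to reproduce. The hazard, the loss and the length of the extension below are assumptions.

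**1. The >12 month formula at a constant hazard.** Take a hazard of 0.01 per patient-year and let every subject stay f years past month 12. The expected value of I_>12/N_>12 is 1 − exp(−0.01 f):

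| Extra follow-up | Expected value |
|---|---|
| 3 months | 0.25% |
| 6 months | 0.50% |
| 12 months | 1.00% |
| 24 months | 1.98% |

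This is about an eight-fold spread with no change in risk.

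**2. The same cases with different follow-up.** Suppose 100 subjects pass month 12. Patient-years are 100 × mean extra years. The SAP columns use an exact (Clopper-Pearson) 95% interval. The zero-case Poisson upper limit is 3.689 / patient-years.

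| Mean extra follow-up | Patient-years | 2 cases, SAP | 2 cases per 100 patient-years | 0 cases, SAP upper limit | 0 cases, Poisson upper limit per 100 patient-years |
|---|---|---|---|---|---|
| 3 months | 25 | 2.0% (0.24 to 7.04) | 8.0 (0.97 to 28.9) | 3.6% | 14.8 |
| 6 months | 50 | same | 4.0 (0.48 to 14.5) | 3.6% | 7.4 |
| 12 months | 100 | same | 2.0 (0.24 to 7.2) | 3.6% | 3.7 |
| 24 months | 200 | same | 1.0 (0.12 to 3.6) | 3.6% | 1.8 |

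The two scales agree only when mean extra follow-up is about 12 months. SAP 10.8.2 names no interval method. A Wald interval for 0/100 would have an upper limit of 0%.

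**3. The 0-12 month formula with loss.** Let λ = 0.01 and μ = −ln(1 − loss), with leaving unrelated to granuloma and cases discontinued as protocol 3.3.1 says. Over one year:

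- cases = λ/(λ+μ) × [1 − exp(−(λ+μ))]
- completers = exp(−(λ+μ))
- SAP figure = cases / (cases + completers)
- true 12-month risk = 1 − exp(−0.01) = 0.995%

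| Loss in year 1 | SAP figure | Ratio to true risk |
|---|---|---|
| 10% | 1.049% | 1.05 |
| 20% | 1.114% | 1.12 |
| 33% | 1.225% | 1.23 |

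The 33% is 1 − 100/150, from up to 150 enrolled and 100 completers. It is an upper illustration, not a planned loss. The ratio hardly depends on the hazard: at 33% loss it is 1.233 for λ = 0.001 and 1.226 for λ = 0.03.

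**4. Zero cases in months 0-12.** The estimate is 0 under every definition, and only the limit moves. With 150 treated and 100 completers, the upper limit is 3.62% on 0/100 and 2.43% on 0/150. It is 3.28 to 2.68 per 100 patient-years if the 50 leavers stay a mean of 3 to 9 months (112.5 to 137.5 patient-years).

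**The case against.** **The worst line is outside the primary endpoint.** This is true. The >12 month formula stands under the SAP's primary endpoint heading, but protocol 3.2.1 ends the endpoint at month 12. A reader might infer that the primary endpoint itself is unusable. The documents do not support that: the 0-12 month figure remains an approximate risk. The >12 month line still serves the rate objective.

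**The first-year bias is small.** This largely stands. Under non-informative leaving the bias is upward, which is conservative for a safety claim. A single case in 101 has an exact interval of 0.03% to 5.4%, far wider than a 23% relative shift. The incidence percentage in SAP 10.8.2, read with SAP 7 and 10.3, is reasonably a percentage of ITT, so an all-treated figure already stands beside the rate. After month 12 it does not help, because it contains no time either.

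**A reader might infer that the formula would hide a real rise at the 12-month interim.** It would do so no more than any other estimator. The protocol synopsis says "Overall duration of the study will be approximately 48 months"; with 36 months per subject, about 12 months remain for enrolment. If 150 subjects enter evenly without loss, the 100th enters at month 8 and reaches month 12 at calendar month 20. The first 100 then average 4 extra months, or 33 patient-years. Expected cases are 0.33 at 1 per 100 patient-years and 1.0 if the hazard triples, so no case at all has probability 72% or 37%. One case would give 3.0 per 100 patient-years (0.08 to 16.7). Sparse data is the limit, and person-time does not cure it.

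**A reader might also infer a steady rise from report to report.** The schedule is not settled enough to say so. SAP 3 plans a 9-month interim and states that "a second interim analysis will be completed after the first cohort of 100 subjects reach 12 months"; SAP 4.1 likewise plans two. SAP 10.8.2 refers to three interim reports, and the annual safety reports in SAP 3 have no listed content. By the final report the period is bounded at months 12 to 36, and what remains is the variable length of the extension.

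**Conclusion.** The point holds and should be fixed. SAP 2.1.1.1 contradicts the SAP's own definition of a rate. After month 12 the contradiction is substantive: the same hazard can give figures eight-fold apart, and a zero-case limit of 3.6% can stand for anything from 14.8 to 1.8 per 100 patient-years. The figure cannot be compared between data cuts, or with the 0-12 month figure unless mean extra follow-up happens to be about 12 months. That follows from the formula; only the sizes rest on the assumed hazard, the 100 subjects and the 25 to 200 patient-years.

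In the fixed windows the fault is one of naming plus a moderate bias, about 5% to 23% relative for 0-12 months at 10% to 33% loss. It is zero if nobody leaves event-free. The direction assumes that leaving is unrelated to granuloma. That is not assured, because protocol 10.0 lists an unresolved significant safety event as a reason for leaving. If no granuloma occurs, only the confidence limits are affected, in every period.

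**What to change.** In SAP 2.1.1.1, 10.3 and 10.8.2:

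- Report subjects with a first confirmed granuloma per 100 patient-years on 3 mg/mL in the ITT population, for 0-9, 0-12 and >12 months. Print the patient-years and give an exact Poisson 95% interval.
- Count actual time from the first 3 mg/mL fill (or month 12) to the earliest of first granuloma, end of 3 mg/mL treatment, last granuloma evaluation, end of interval or data cut.
- Assign a case to 0-12 or >12 months by actual date, since visits may fall 7 days either side of schedule. SAP 8.2 uses nominal times for summaries and excludes unscheduled follow-up data from statistical analyses; exempt granuloma findings from both rules.
- Keep the present ratios as supportive figures labelled proportions, with an exact binomial interval. Note that the PP 0-12 month figure omits cases discontinued before month 12, because SAP 6 requires at least 12 months of therapy.
- Reconcile the two interim analyses of SAP 4.1 with the three interim reports of SAP 10.8.2, and say which reports carry the >12 month rate.
- Kaplan-Meier estimates at 12 and 36 months are optional.

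Align protocol 14.2, which limits the granuloma assessment to 12-month completers, with the ITT analysis.

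The cost is SAP wording, one sentence in the protocol and a little programming. Administration dates are on the CRF (SAP 9.4), refill dates are listed (SAP 10.1), and a final visit is required at discontinuation (protocol 9.4). Protocol 10.0 names only the reason for discontinuation as a CRF item, so confirm that the date 3 mg/mL treatment ended is captured, or use the final visit date. The downside is a less familiar unit and reliance on non-informative censoring, which the SAP should state.
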